6.9.1. Coprimary Outcomes and Primary Analysis Methodology

The coprimary outcomes are:

- Proportion of patients achieving sPGA (0,1) at Week 12, and
- Proportion of patients achieving PASI 75 at Week 12.

The primary analysis will be based on the ITT population for the Induction Dosing Period (Period 2) comparing each ixekizumab dose regimen and placebo at Week 12 (Visit 7). The primary analysis is logistic regression analysis with treatment as a factor (Section 6.1.2). Missing data will be imputed using the NRI method (Section 6.2.1).

The coprimary comparisons will be tested based on the gatekeeping testing procedure detailed in Section 6.3.

6.9.2. Major Secondary Efficacy Analyses

The major secondary outcomes are:

- Proportion of patients achieving sPGA (0) at Week 12 (Visit 7)
- Proportion of patients achieving PASI 90 at Week 12 (Visit 7)
- Proportion of patients achieving PASI 100 at Week 12 (Visit 7)
- Change from baseline in NAPSI score at Week 12 (Visit 7)
- Proportion of patients maintaining an sPGA (0,1) from Week 12 (Visit 7) after re-randomization at start of Maintenance Dosing Period to Week 60 (Visit 19) for ixekizumab-treated patients who had an sPGA (0,1) at Week 12 and were re-randomized
- Proportion of patients maintaining or achieving an sPGA (0) from Week 12 (Visit 7) after re-randomization at start of Maintenance Dosing Period to Week 60 (Visit 19) for ixekizumab-treated patients who had an sPGA (0,1) at Week 12 and were re-randomized

The major secondary analyses will be based on the ITT population for the Induction Dosing Period (Period 2) at Week 12 (Visit 7) and based on the Maintenance Dosing Period Primary population for the Maintenance Dosing Period (Period 3) at Week 60 (Visit 19). The analysis for categorical efficacy outcomes will be logistic regression analysis with treatment as a factor with NRI (Section 6.1.2, Section 6.1.3.1, Section 6.2.1). The analysis for continuous efficacy outcomes will use MMRM with treatment, baseline value, visit, treatment-by-visit, and baseline-by-visit interactions as fixed factors (Section 6.1.2).

The major secondary comparisons will be tested based on the gatekeeping multiple testing procedure detailed in Section 6.3.

6.9.3. Additional Analyses of Co-Primary Outcomes

There will be no adjustment for multiple comparisons for additional analyses of the co-primary outcomes.

To support the primary efficacy analysis, the coprimary outcomes, sPGA (0,1) and PASI 75, will be analyzed based on the PPS population for the Induction Dosing Period (Period 2) at Week 12

(Visit 7) using a logistic regression analysis with treatment as a factor (Section 6.1.2). Missing data will be imputed using the NRI method (Section 6.2.1). A categorical MMRM analysis with treatment, baseline value, visit, treatment-by-visit and baseline-by-visit interactions as fixed factors will be also be done (Section 6.1.2).

The time to first sPGA (0,1) response, and the time to first PASI 75 response will be assessed based on the ITT Population during Period 2 as described in Section 6.1.2. Figures showing the proportion of patients achieving an sPGA (0,1) response and a PASI 75 response at each scheduled visit during Period 2 within each treatment group in the ITT population (including Week 12, NRI) will be provided.

Figures showing the proportion of patients maintaining an sPGA (0,1) response and maintaining a PASI 75 response at each scheduled visit during Period 3 (including Week 60, NRI) within each treatment group in the Maintenance Dosing Period Primary Population will also be provided.

Please see [Table RHBH. 6.5.](#) for details of other additional analyses for co-primary outcomes.

6.9.4. Other Secondary Efficacy Analyses

There will be no adjustment for multiple comparisons for other secondary efficacy analyses.

6.9.4.1. Period 2 (Induction Dosing Period)

Other secondary analyses will be done on sPGA (0), PASI 50, PASI 90, PASI 100, NAPSI score = 0, PPSI score = 0, PPASI 50, PPASI 75, PPASI 100, PASI change from baseline, PASI percent improvement from baseline, BSA change from baseline, NAPSI change from baseline, PSSI change from baseline, PPASI change from baseline. Comparisons of Ixekizumab treatment groups and placebo will be provided for Week 12 and all other postbaseline visits in Period 2.

[Table RHBH. 6.5.](#) provides the detailed analyses including analysis type, method and imputation, population, time point, and treatment comparisons for other secondary analyses.

6.9.4.2. Period 3 (Maintenance Dosing Period)

6.9.4.2.1. Maintenance Dosing Period Primary Population

Other secondary analyses will be done on sPGA (0), PASI 90, PASI 100, NAPSI score = 0, PPSI score = 0, PPASI 50, PPASI 75, PPASI 100, PASI change from baseline, PASI percent improvement from baseline, BSA change from baseline, NAPSI change from baseline, PSSI change from baseline, PPASI change from baseline. Comparisons of ixekizumab treatment groups and placebo will be provided for Week 60 and all other postbaseline visits in Period 3. A categorical MMRM analysis for selected variables with treatment, baseline value, visit, treatment-by-visit and baseline-by-visit interactions as fixed factors will be also be done (Section 6.1.3.1).

The time to relapse (loss of response; sPGA ≥ 3) during Period 3 will be assessed based on the Maintenance Dosing Period Primary Population as described in Section 6.1.3.1.

The number and percentage of placebo patients experiencing disease rebound within 8 weeks (worsening of Ps severity over baseline sPGA score, *or* worsening of Ps severity over baseline PASI score by 125%, *or* change in Ps phenotype [for example, from plaque to pustular]) after re-randomization to placebo at Week 12 will be summarized.

[Table RHBH. 6.5.](#) provides the detailed analyses including analysis type, method and imputation, population, time point, and treatment comparisons for other secondary analyses.

6.9.4.2.2. Maintenance Dosing Period Secondary Population

The number and percentage of patients achieving or maintaining categorical efficacy outcome responses (sPGA (0,1), sPGA (0), PASI 75, PASI 90, PASI 100, PPASI 50, PPASI 75, PPASI 100) will be summarized by treatment group for all scheduled visits during Period 3, including Week 60 (NRI).

The change from baseline and percent improvement in PASI scores, the change from baseline in BSA, NAPSI scores, PSSI scores and PPASI scores will be summarized using descriptive statistics.

6.9.4.2.3. Maintenance Dosing Period Relapse Population

For patients who were retreated with ixekizumab following loss of response (relapse), the proportion of patients regaining or achieving categorical efficacy outcome responses (that is, sPGA (0,1), sPGA (0), PASI 75, PASI 90, PASI 100) within 12 weeks after ixekizumab retreatment will be summarized using descriptive statistics by treatment group.

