**12.2.6.3.2. Period 3 (Maintenance Dosing Period)**

Unless otherwise specified, the other secondary analyses during Period 3 will be based on the Maintenance Dosing Period Primary Population.

Time to loss of response (that is, relapse defined as an sPGA score of  $\geq 3$ ) is defined as the number of days from the Week 12 re-randomization to the first visit at which the patient has an sPGA score of  $\geq 3$  during Period 3. For patients who discontinue early in Period 3 or who complete Period 3 without meeting the criteria, the time to loss of response will be censored and defined as the number of days from Week 12 re-randomization to the patient's last visit during Period 3. Time to loss of response for each treatment group in Period 3 will be estimated using the Kaplan-Meier product limit method. Treatment group comparisons will be performed using the log-rank test.

The proportion of patients who meet sPGA (0), PASI 75, PASI 90, PASI 100 criteria, and any other categorical efficacy endpoint will be summarized at each visit. Treatment group comparisons will be performed using the logistic regression model described in Section 12.2.1.2 and a Fisher's exact test when appropriate. Missing data will be imputed using the NRI method described in Section 12.2.1.4.1.

For all continuous efficacy variables that are collected at repeated visits, treatment group comparisons will be analyzed at each visit using the MMRM model described in Section 12.2.1.2 when appropriate. The Week 60 (Visit 19) comparison will be the main interest, and those at earlier time points will be considered secondary.

For patients who were retreated with ixekizumab following loss of response (relapse), the following analyses will be performed:

- The proportion of patients who regain an sPGA (0, 1) and an sPGA (0) within 12 weeks after ixekizumab retreatment will be summarized by the original re-randomization treatment group.
- The proportion of patients who achieve a PASI 75, PASI 90, and PASI 100 within 12 weeks after ixekizumab retreatment will be summarized by the original re-randomization treatment group.

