5.2. Method of Assignment to Treatment

At Week 0 (Visit 2), patients who meet all criteria for enrollment at Visits 1/1A and 2 will be randomized at a 2:2:1 ratio to ixekizumab 80 mg Q2W, ixekizumab 80 mg Q4W, or placebo. Assignment to double-blind treatment groups will be determined by a computer-generated random sequence using an interactive web response system (IWRS). The IWRS will be used to assign double-blind investigational product to each patient. Site personnel will confirm that they have located the correct assigned investigational product package by entering a confirmation number found on the package into the IWRS.

At Week 12 (Visit 7), patients who enter Period 3 will be classified as a responder (sPGA score of 0 or 1) or non-responder (sPGA score of >1). Patients who received ixekizumab during Period 2 and who are responders will be re-randomized at a 2:1 ratio to 80 mg Q4W or placebo using the IWRS. Patients will be stratified by ixekizumab induction dosing regimen (80 mg Q2W or 80 mg Q4W). Patients who received placebo during Period 2 and who are responders will be assigned to continue to receive placebo until relapse occurs. Relapse (loss of response) is defined as an sPGA score of ≥ 3 . Non-responders who received any investigational product (assigned to any treatment group) during Period 2 will be assigned to receive treatment with 80 mg ixekizumab Q4W. Assignment to treatment will be determined by the IWRS.

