6.1.3. General Considerations for Analyses during Period 3 (Maintenance Dosing Period)

Period 3 starts at the first injection of study treatment at Week 12 (Visit 7) and ends on the date of Week 60 (Visit 19) or the date of the ETV (if it occurs between Weeks 12 and 60).

For Period 3 efficacy and health outcomes analyses, baseline is defined as the last non-missing assessment recorded on or prior to the date of first injection of study treatment at Week 0 (Visit 2). In most cases, this will be the measure recorded at Week 0 (Visit 2).

Unless otherwise specified, for Period 3 safety analyses, baseline and baseline period are defined as the last non-missing assessment prior to the first injection of study treatment at Week 12 (Visit 7). In most cases, this will be the measure recorded at Week 12 (Visit 7). For treatment-emergent adverse events, baseline is the event started prior to the study drug injection at Week 12 (Visit 7) and continued into Period 3.

For patients who met relapse criteria (loss of response; sPGA ≥ 3) and were retreated with ixekizumab, only data up to the time of relapse will be included in the maintenance of effect analyses. These patients will be considered non-responders to categorical assessments per the NRI imputation method (see Section 6.2.1).

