6.1.3.3. Maintenance Dosing Period Relapse Population

For patients who were retreated with ixekizumab following loss of response (relapse), the proportion of patients maintaining or achieving categorical efficacy and health outcome responses (that is, sPGA (0,1), sPGA (0), PASI 75, PASI 90, PASI 100) within 12 weeks after ixekizumab retreatment will be summarized by treatment group. For the safety analyses on the

Maintenance Dosing Period Relapse population with ixekizumab retreatment, baseline is defined as the last non-missing assessment on or prior to the first dose of re-treatment. The treatment period for the Maintenance Dosing Period Relapse population with ixekizumab retreatment starts at the time of the relapse visit (first dose of re-treatment) and ends on the date of Week 60 (Visit 19) or the ETV (if it occurs between the relapse visit and Week 60).

The categorical safety measures will be summarized with incidence rates.

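### PASI 75 and PASI 90 after retreatment count relapsers who never lost that response, so they overstate recapture if read that way

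*SAP*

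**What the plan says.** Relapse rests on the physician's global score alone. SAP section 5.2 states: "Relapse (loss of response) is defined as an sPGA score of" 3 or more. Protocol section 7.1.3 and the Relapse Population definition in SAP section 6.1.1 agree, and none of them adds a PASI or body-surface condition.

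For Period 3 efficacy, SAP section 6.1.3 says "baseline is defined as the last non-missing assessment recorded on or prior to the date of first injection of study treatment at Week 0". SAP section 6.1.3.3 defines a second baseline, at the first retreatment dose, but for safety analyses only. PASI response after retreatment is therefore still measured against Week 0.

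The retreatment summary is described in three places:

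- Protocol section 12.2.6.3.2, for sPGA: "The proportion of patients who regain an sPGA (0, 1) and an sPGA (0) within 12 weeks after ixekizumab retreatment". For PASI: "The proportion of patients who achieve a PASI 75, PASI 90, and PASI 100 within 12 weeks after ixekizumab retreatment".
- SAP section 6.1.3.3: "proportion of patients maintaining or achieving categorical efficacy and health outcome responses".
- SAP section 6.9.4.2.3: "proportion of patients regaining or achieving categorical efficacy outcome responses".

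All three cover every retreated relapser. None requires that the PASI level was lost before retreatment. SAP Table RHBH 6.1 lists no comparison for the Relapse Population, and SAP section 6.9.4 makes no multiplicity adjustment for other secondary efficacy analyses.

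**The concern.** The two scales measure different things. As SAP Table RHBH 6.4 describes them, sPGA grades plaques on induration, redness and scaling, while PASI multiplies severity by the area involved in each region. A patient who relapses with a few moderate plaques can reach sPGA 3 and still be at least 75% better than at Week 0 on PASI. That patient enters the numerator for PASI 75 even if retreatment does nothing.

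The stated objective is the efficacy of ixekizumab after relapse. With no comparator group, nothing offsets such an error. The two SAP sections also point in different directions: *maintaining* openly admits responses that were never lost, while *regaining* invites the reader to take the figure as recapture.

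**Working it through.** **The plan's own figures.** The documents give no expected retreatment response. The nearest planning figure is the maintenance sample size in Protocol section 12.1 and SAP section 5.3. It reproduces: 420 × 2/5 = 168 per ixekizumab arm; 168 × 0.70 = 117.6; split 2:1 this is 78.4 and 39.2, stated as 78 and 39. For 70% against 10%, with two-sided Fisher's exact test at 0.025, exact power is above 0.9999, so the stated >99% holds.

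**Can sPGA 3 coexist with PASI 75 or 90?** Inputs: the PASI formula in SAP Table RHBH 6.4 (region weights: head 0.1, upper limbs 0.2, trunk 0.3, lower limbs 0.4) and the minimum baseline PASI of 12 (Protocol section 8.1, criterion 4). Assumption: sPGA 3 goes with PASI component scores of 2. Both are labelled moderate, but the SAP does not equate the scales, so scores of 3 are shown too. PASI = (sum of three components) × (area grade) × (sum of weights). PASI 75 is kept if baseline ≥ PASI/0.25, and PASI 90 if baseline ≥ PASI/0.10.

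| Relapse pattern | Components | Area grade | PASI | Baseline to keep PASI 75 | Baseline to keep PASI 90 |
|---|---|---|---|---|---|
| Upper limbs | 2 | 1 | 1.2 | 4.8 | 12 |
| Trunk | 2 | 1 | 1.8 | 7.2 | 18 |
| Lower limbs | 2 | 1 | 2.4 | 9.6 | 24 |
| Upper and lower limbs | 2 | 1 | 3.6 | 14.4 | 36 |
| All four regions | 2 | 1 | 6.0 | 24 | 60 |
| Lower limbs | 2 | 2 | 4.8 | 19.2 | 48 |
| Trunk | 3 | 1 | 2.7 | 10.8 | 27 |
| Lower limbs | 3 | 1 | 3.6 | 14.4 | 36 |
| All four regions | 3 | 1 | 9.0 | 36 | not reachable (90 exceeds the scale maximum of 72) |

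For example, PASI 2.4 against a baseline of 12 is (12 − 2.4)/12 = 80% improvement. So the overlap is possible for limited-area relapse and fades as area or severity rises.

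**Which measures are exposed?** sPGA (0,1) and sPGA (0) are lost by definition at sPGA ≥3. PASI 100 needs a PASI of 0, which means no psoriasis and cannot go with sPGA ≥3. Only PASI 75 and PASI 90 remain.

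**Size.** Let q be the share of retreated relapsers still at the PASI level at relapse, and r the true recapture among the rest. If the first group is always counted, the reported rate is q + (1 − q)r and the excess over r is q(1 − r). Excess in percentage points:

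| q | r = 0.9 | r = 0.7 | r = 0.5 |
|---|---|---|---|
| 0 | 0 | 0 | 0 |
| 0.05 | 0.5 | 1.5 | 2.5 |
| 0.10 | 1 | 3 | 5 |
| 0.20 | 2 | 6 | 10 |
| 0.30 | 3 | 9 | 15 |
| 0.40 | 4 | 12 | 20 |

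**In patients.** Across both induction arms, 2 × 39 = 78 are re-randomised to placebo. If 90% do not maintain response, 78 × 0.90 = 70.2, so at most about 70 relapse. That is an upper bound, because patients at sPGA 2 and dropouts also count as not maintaining. With q = 0.20, 14 still hold PASI 75 and 56 have lost it:

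- r near 0.80: 45/56 = 80.4% true recapture; reported (45 + 14)/70 = 84.3%.
- r near 0.60: 34/56 = 60.7% true recapture; reported (34 + 14)/70 = 68.6%.

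**The case against.** The strongest reply is that the PASI measure was never meant as recapture. The protocol says patients *regain* sPGA but *achieve* PASI levels, in the objectives (section 6.2.2) and again in the analysis section, and the SAP objectives (section 4.2.2) keep that distinction. On this reading the PASI figure is response status after retreatment, and the loss-and-regain measure already exists in sPGA (0,1), which matches the relapse definition. This stands: the planned summary is valid for what the protocol calls it and should not be replaced. Nor should *regain* be written throughout. Entry to re-randomisation needs only sPGA 0 or 1, so some patients may first reach PASI 90 or 100 after retreatment. What the reply does not remove is the conflict between the two SAP sections, or the lack of any figure showing how many PASI successes were present before retreatment.

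Three stronger readings are tempting, and the documents do not support them:

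- A reader might infer that limited-area relapse always keeps PASI 75. The tables show this depends on the assumed component scores, the area grade and the baseline PASI.
- A reader might infer that success can be scored at the relapse visit itself, because SAP section 6.1.3.3 starts a treatment period there. That sentence follows the safety baseline; the efficacy text refers to the 12 weeks after retreatment.
- A reader might infer that the whole set of retreatment results is inflated. PASI 100 and both sPGA measures cannot be affected in this way.

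**Conclusion.** The point holds for PASI 75 and, less often, PASI 90. As planned, relapsers who still hold the level count as retreatment successes regardless of retreatment, and read as recapture the rate is overstated by q(1 − r). That is 0 to 20 points for q of 0 to 0.40 and r of 0.5 to 0.9, and 1 to 10 points for q of 0.10 to 0.20. These ranges are assumptions. The documents give no value for q or r, so it cannot be said that the rate will be inflated, only that it can be and in one direction. The formula also assumes that every patient still at the level at relapse is counted at some visit within the 12 weeks.

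The consequence is limited. This is a descriptive other-secondary summary with no comparison and no alpha, and no primary or major secondary conclusion rests on it. It is worth correcting because the correction is cheap and the affected figure bears directly on how well retreatment works.

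**What to change.** In SAP sections 6.1.3.3 and 6.9.4.2.3 and Table RHBH 6.5:

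1. Use one wording in both sections, in line with the protocol: regain for sPGA, achieve for PASI.
2. Keep the protocol-defined summary of PASI levels achieved within 12 weeks over all retreated relapsers.
3. Tabulate how many retreated relapsers still met PASI 75 and PASI 90 at the relapse visit.
4. Add the PASI 75 and PASI 90 rates within 12 weeks among retreated relapsers who did not meet that level at the relapse visit, counting only assessments after the first retreatment dose. PASI 100 needs no such restriction.
5. Keep regain of sPGA (0,1) as the main retreatment measure.

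No new data are needed, since PASI is scheduled at every Period 3 visit (Protocol Attachment 1). The cost is one extra table, smaller denominators and a PASI figure that may be less favourable.

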6.10. Health Outcomes/Quality of Life Analyses

The health outcomes and quality of life (QoL) measures are Itch NRS, DLQI, SF-36 MCS and PCS, patient's global assessment of disease severity (PatGA) and Joint Pain VAS.

[Table RHBH. 6.6.](#) includes the description and derivation of the health outcomes and QoL measures.

[Table RHBH. 6.7.](#) provides the detailed analyses including analysis type, method and imputation, population, time point, and treatment group comparisons for health outcomes and QoL analyses.

Table RHBH. 6.6. Description and Derivation of Health Outcomes and Quality-of-Life Measures

Measure / Description	Variable	Derivation / Comment	Imputation Approach if with Missing Components

Itch Numeric Rating Scale (NRS): Itch NRS is a single-item, patient-reported outcome (PRO) measure designed to capture information on the overall severity of a patient’s itching due to their psoriatic skin condition by having the patient circle the integer that best describes the worst level of itching in the past 24 hours on an 11-point NRS anchored at 0 representing “no itching” and 10 representing “worst itch imaginable.”
	Itch NRS score	Range from 0 to 10.	Single item, missing if missing
	Itch NRS change from baseline	Calculated as: observed Itch NRS – baseline Itch NRS	Missing if baseline or observed value is missing
	Itch NRS ≥4 improvement from baseline	Reduced/decreased of ≥4 point from baseline	Missing if baseline or observed value is missing
	Itch NRS =0	Defined as a post-baseline Itch NRS score of 0	Missing if Itch NRS score is missing

Dermatology Life Quality Index (DLQI): DLQI is a validated, dermatology-specific, patient-reported measure that evaluates patient’s health-related QoL. This questionnaire has 10 items that are grouped in 6 domains, including symptoms and feelings, daily activities, leisure, work and school, personal relationships, and treatment. The recall period of this scale is over the “last week”. Response categories and corresponding scores are: Very much = 3 A lot = 2 A little = 1 Not at all = 0 Not relevant = 0
	DLQI symptoms and feelings domain	Sum of responses of questions #1 and #2: #1. How itchy, sore, painful or stinging has your skin been? #2. How embarrassed or self-conscious have you been because of your skin?	If one question in a domain is missing, that domain is missing.
	DLQI daily activities domain	Sum of responses of questions #3 and #4: #3. How much has your skin interfered with you going shopping or looking after your home or garden? #4. How much has your skin influenced the clothes you wear?	If one question in a domain is missing, that domain is missing.
	DLQI leisure domain	Sum of responses of questions #5 and #6: #5. How much has your skin affected any social or leisure activities? #6. How much has your skin make it difficult for you to do any sport?	If one question in a domain is missing, that domain is missing.
	DLQI work and school domain	Sum of responses of questions question #7A and #7B: #7A. Has your skin prevented you from working or studying? #7B. If No: how much has your skin been a problem at work or studying?	If the answer to question #7A is missing, this domain is missing. If #7A is No, and #7B is missing, this domain is missing.

Measure / Description	Variable	Derivation / Comment	Imputation Approach if with Missing Components
	DLQI personal relationships domain	Sum of responses of questions #8 and #9: #8. How much has your skin created problems with your partner or any of your close friends or relatives? #9. How much has your skin caused any sexual difficulties?	If one question in a domain is missing, that domain is missing.
	DLQI treatment	Response of question #10: #10. How much of a problem has the treatment for your skin been, for example by making your home messy, or by taking up time?	If one question in a domain is missing, that domain is missing.
	DLQI total score	A DLQI total score is calculated by summing all 10 question responses, and has a range of 0 to 30 (less to more impairment) (Finlay and Khan 1994; Basra et al. 2008).	If two or more questions are missing, the total score is missing. Note: #7B could be a valid missing while #7A is not “No.” That is, #7 should be considered as one question.
	DLQI (0,1)	A DLQI (0,1) response is defined as a post-baseline DLQI total score of 0 or 1. A DLQI total score of 0 to 1 is considered as having no effect on a patient’s HRQoL (Khilji et al. 2002; Hongbo et al. 2005).	Missing if DLQI total score is missing
	DLQI total score and domain scores change from baseline	Calculated as: observed DLQI (total score or domain scores) – baseline DLQI (total score or domain scores)	Missing if baseline or observed value is missing

Measure / Description	Variable	Derivation / Comment	Imputation Approach if with Missing Components

Medical Outcomes Study 36-item Short-Form Health Survey (SF-36):
 
The SF-36 is a 36-item patient-administered measure designed to be a short, multipurpose assessment of health in the areas of physical functioning, role–physical, role–emotional, bodily pain, vitality, social functioning, mental health, and general health. The 2 overarching domains of mental well-being and physical well-being are captured by the Mental Component Summary and Physical Component Summary scores. The summary scores range from 0 to 100; higher scores indicate better levels of function and/or better health. Items are answered on Likert scales of varying lengths. The SF-36 version 2 (acute version) will be used, which utilizes a 1-week recall period (Ware [2000]).
	
8 associated domain scores (scaled score and t-score):
 
 • Physical Functioning, • Role Physical, • Bodily Pain, • General Health, • Vitality, • Social Functioning, • Role Emotional, • Mental Health 
2 component Scores (t-score):
 
 • MCS Score • PCS Score 	
Per copyright owner, the QualityMetric Health Outcomes™ Scoring Software will be used to derive SF-36 domain and component scores. After data quality-controls, the SF-36 software will re-calibrate the item-level responses for calculation of the domain and component scores. These raw scores will be transformed into the domain scores (t-scores) using the 1-week recall period. The summary scores range from 0 to 100.
	
If an item is missing, there will be imputation conducted by the Scoring Software.

	
PCS, MCS scores change from baseline
	
Calculated as: observed score – baseline score
	
Missing if baseline or observed value is missing

Patient’s Global Assessment of Disease Severity
	
PatGA score
	
Range from 0 to 5.
	
Single item, missing if missing

Measure / Description	Variable	Derivation / Comment	Imputation Approach if with Missing Components

(PatGA): PatGA is a single-item, patient-reported outcome (PRO) measure designed to capture information on the overall severity of a patient’s psoriasis by having the patient circle the integer that best describes their disease ‘today’ on a 6-point NRS anchored at 0 (clear), 1, 2, 3, 4, or 5 (severe).
	PatGA change from baseline	Calculated as: observed PatGA – baseline PatGA	Missing if baseline or observed value is missing

Joint Pain Visual Analog Scale (VAS): Joint Pain VAS is a patient-administered scale designed to measure current joint pain from psoriatic arthritis (PsA) using a 100-mm horizontal VAS. Overall severity of a patient’s joint pain from PsA at the present time is indicated by placing a single mark on the horizontal scale (0 = none; 100 = as severe as you can imagine).
	Joint Pain VAS	Range from 0 to 100. Note: higher value indicates greater severity of illness.	Single item, missing if missing
	Joint Pain VAS change from baseline	Calculated as: observed Joint Pain VAS – baseline Joint Pain VAS	Missing if baseline or observed value is missing
	Joint Pain VAS =0	Defined as a post-baseline Joint Pain VAS of 0	Missing if Joint Pain VAS is missing

Abbreviations: MCS = mental component summary; NRS = Numeric Rating Scale; PCS = physical component summary; PRO = patient reported outcome; SF-36 = Medical Outcomes Study 36-Item Short-Form Health Survey; VAS = visual analog scale.

Table RHBH. 6.7. Description of Health Outcomes and Quality-of-Life Analyses

Variable	Analysis Method (Sections 6.1 and 6.2)	Population (Section 6.1.1)	Comparison / Time Point
Itch NRS			
Itch NRS ≥ 4 improvement from baseline — Major secondary	Logistic regression analysis with NRI; Fisher's exact test with NRI	ITT population - patients with baseline Itch NRS score ≥ 4	IXE80Q2W & IXE80Q4W vs. PBO at Week 12 and all other post-baseline visits in Period 2
	Logistic regression analysis with NRI; Fisher's exact test with NRI	Maintenance Dosing Period Primary Population - patients with baseline Itch NRS score ≥ 4	IXE80Q2W/IXE80Q4W vs. IXE80Q2W/PBO, IXE80Q4W/IXE80Q4W vs. IXE80Q4W/PBO and IXE/IXE vs IXE/PBO at Week 60 and all other postbaseline visits in Period 3
Itch NRS change from baseline	MMRM	ITT population	IXE80Q2W & IXE80Q4W vs. PBO at Week 12 and all other post-baseline visits in Period 2
	MMRM	Maintenance Dosing Period Primary Population	IXE80Q2W/IXE80Q4W vs. IXE80Q2W/PBO, IXE80Q4W/IXE80Q4W vs. IXE80Q4W/PBO and IXE/IXE vs IXE/PBO at Week 60 and all other postbaseline visits in Period 3
DLQI			
DLQI (0,1)	Logistic regression analysis with NRI; Fisher's exact test with NRI	ITT population	IXE80Q2W & IXE80Q4W vs. PBO at Week 12 and all other post-baseline visits in Period 2
	Logistic regression analysis with NRI; Fisher's exact test with NRI	Maintenance Dosing Period Primary Population	IXE80Q2W/IXE80Q4W vs. IXE80Q2W/PBO, IXE80Q4W/IXE80Q4W vs. IXE80Q4W/PBO and IXE/IXE vs IXE/PBO at Week 60 and all other postbaseline visits in Period 3
DLQI total score change from baseline — Major secondary	MMRM; ANCOVA with LOCF	ITT population	IXE80Q2W & IXE80Q4W vs. PBO at Week 12 and all other post-baseline visits
	MMRM; ANCOVA with LOCF	Maintenance Dosing Period Primary Population	IXE80Q2W/IXE80Q4W vs. IXE80Q2W/PBO, IXE80Q4W/IXE80Q4W vs. IXE80Q4W/PBO and IXE/IXE vs IXE/PBO at Week 60 and all other postbaseline visits in Period 3
DLQI domain scores change from baseline			
36 item Short Form Health Survey (SF-36)			
SF-36 PCS, MCS, domain scores change from baseline	MMRM	ITT Population	IXE80Q2W & IXE80Q4W vs. PBO at Week 12 and all other post-baseline visits
	MMRM	Maintenance Dosing Period Primary Population	IXE80Q2W/IXE80Q4W vs. IXE80Q2W/PBO, IXE80Q4W/IXE80Q4W vs. IXE80Q4W/PBO and

Variable	Analysis Method (Sections 6.1 and 6.2)	Population (Section 6.1.1)	Comparison / Time Point
			IXE/IXE vs IXE/PBO at Week 60 and all other postbaseline visits in Period 3
Patient's Global Disease Assessment (PatGA)			
PatGA score change from baseline	MMRM	ITT Population	IXE80Q2W & IXE80Q4W vs. PBO at Week 12 and all other post-baseline visits
	MMRM	Maintenance Dosing Period Primary Population	IXE80Q2W/IXE80Q4W vs. IXE80Q2W/PBO, IXE80Q4W/IXE80Q4W vs. IXE80Q4W/PBO and IXE/IXE vs IXE/PBO at Week 60 and all other postbaseline visits in Period 3
Joint Pain VAS			
Joint Pain VAS change from baseline	MMRM	ITT population - patients with baseline psoriatic arthritis	IXE80Q2W & IXE80Q4W vs. PBO at Week 12 and all other post-baseline visits
	MMRM	Maintenance Dosing Period Primary Population - patients with baseline psoriatic arthritis	IXE80Q2W/IXE80Q4W vs. IXE80Q2W/PBO and IXE80Q4W/IXE80Q4W vs. IXE80Q4W/PBO at Week 60 and all other postbaseline visits in Period 3

Abbreviations: ANCOVA = analysis of covariance; DLQI = Dermatology Life Quality Index; ITT = intent-to-treat; LOCF = last observation carried forward; MMRM = mixed-effects model of repeated measures; NRI = nonresponder imputation; NRS = Numeric Rating Scale; VAS = visual analog scale.

